14. CHANGES IN THE PLANNED ANALYSES

No deviations in the conduct of the study or the planned analysis are anticipated. Should any deviations from the analyses specified in the authorized statistical analysis plan arise, such deviations will be documented in the final clinical study report.

15. LIST AND SAMPLES OF TABLES, FIGURES AND GRAPHS

The following lists of tables might not be exhaustive. Additional tables can be produced if necessary.

For each comparison of the various quantitative endpoints (visit 2 versus visit 1 and visit 3 versus visit 1) the descriptive statistics of the endpoint at the two visits will first be calculated and then the P-value will be calculated to assess the statistical significance of the difference. This difference will also be reported as a percentage from baseline.

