8.1 Discontinuation procedures

For any patient discontinuing the observational study, the Investigator will:

- Ask the patient to undergo, as far as possible, an Early Termination Visit (ETV) to examine the patient's health conditions. This examination will verify that all values tested at screening have remained within a clinically acceptable range (i.e. not clinically significant changes compared to screening);
- Arrange for alternative medical care of the withdrawn patient, if necessary;
- Report in the eCRF the date and time of administration of the last dose and the date and primary reason of study discontinuation.

9. Screening Failure

Screening Failures are considered “Potential subjects who were screened for the participation in the clinical investigation, but were not enrolled”.

Primary reason for screening failure could be:

- Adverse Event;
- Patient Non-compliance;
- Withdrawn of Consent;
- Inclusion / exclusion criteria not met;
- Other.

10. Primary objective

- 25% increase of Tear film break-up time with fluorescein (TFBUT) at Study Termination Visit (*Day 35 ± 4 of treatment*) compared to Visit 1 (*Day 0 of treatment - baseline*).

11. Secondary objective

- Evaluation of the change in total score (score from 6 to 33, considering a normal score 0-33) resulting from the sum of the corneal staining score (score from 0 to 15) and conjunctival staining score (score from 0 to 18) with fluorescein using the National Eye Institute Scale (NEI) at Visit 2 (*Day 14 ± 2 of treatment*) and at the Study Termination Visit (*Day 35 ± 4 of treatment*) compared to Visit 1 (*Day 0 of treatment - baseline*);
- To evaluate the tear film stability per group as objectified by the tear break up time with fluorescein (TFBUT) at Study Termination Visit (*Day 35 ± 4 of treatment*) compared to Visit 2 (*Day 14 ± 2 of treatment*).
- Changes about Best Corrected Visual Acuity (BCVA) measured by the “*Early Treatment Diabetic Retinopathy Study*” (ETDRS) at Visit 2 (*Day 14 ± 2 of treatment*) and Study Termination Visit (*Day 35 ± 4 of treatment*) compared to Visit 1 (*Day 0 of treatment - baseline*).
- Patient reported outcomes:
To compare patients reported outcomes (PRO) measures per group, including:
 - Patient's reported symptoms (SANDE) at Visit 2 (*Day 14 ± 2 of treatment*) and Study Termination Visit (*Day 35 ± 4 of treatment*) compared to Visit 1 (*Day 0 of treatment - baseline*).

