3.2. Secondary objective

The secondary objectives were:

Clinical Performance

- Evaluation of the change in total score (score from 6 to 33, considering a normal score 0-33) resulting from the sum of the corneal staining score (score from 0 to 15) and conjunctival staining score (score from 0 to 18) with fluorescein using the National Eye Institute Scale (NEI) at Visit 2 (*Day 14 ± 2 of treatment*) and at the Study Termination Visit (*Day 35 ± 4 of treatment*) compared to Visit 1 (*Day 0 of treatment - baseline*);
- Evaluation of the tear film stability per group as objectified by the tear break up time with fluorescein (TFBUT) at Study Termination Visit (*Day 35 ± 4 of treatment*) compared to Visit 2 (*Day 14 ± 2 of treatment*).
- Changes about Best Corrected Visual Acuity (BCVA) measured by the “*Early Treatment Diabetic Retinopathy Study*” (ETDRS) at Visit 2 (*Day 14 ± 2 of treatment*) and Study Termination Visit (*Day 35 ± 4 of treatment*) compared to Visit 1 (*Day 0 of treatment – baseline*).

Patient reported outcomes

- To compare patients reported outcomes (PRO) measures per group, including:
 - Patient's reported symptoms (SANDE) at Visit 2 (*Day 14 ± 2 of treatment*) and Study Termination Visit (*Day 35 ± 4 of treatment*) compared to Visit 1 (*Day 0 of treatment – baseline*).
 - Evaluation of the degree of satisfaction to the treatment reported by patients through the use of the visual analogue scale (VAS) ##, at the Study Termination Visit (*Day 35 ± 4 of treatment*).
 - Assessment of the quality of life (QOL) ### by “Questionnaire about Eye Symptoms and Daily Life” (DEQS) at Study Termination Visit (*Day 35 ± 4 of treatment*) compared to Visit 1 (*Day 0 of treatment - baseline*).

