5.2. Secondary Endpoints

- Reduction from baseline (*Visit 1- Day 0 of treatment*) in the corneal and conjunctival fluorescein staining score using the NEI scale.

Fluorescein staining of the ocular surface is assessed as the total sum of the corneal and conjunctival subregions.

- Corneal Fluorescein Staining (NEI score, sum of 5 subregions, maximum score 15. Each subregion will have a maximum score of 3.

(0=no staining, 3 = maximum staining).

- Conjunctival Fluorescein Staining (NEI score, sum of 6 subregions, maximum score 18. Each subregion will have a maximum score of 3.

(0=no staining, 3 = maximum staining).

[Time frame: Visit 1, Visit 2 and Study Termination Visit].

- Tear film break-up time with fluorescein (TFBUT)[◊]. [Time frame: Visit 2 and Study Termination Visit].

- BCVA is measured using the standard Early Treatment Diabetic Retinopathy Study (ETDRS) acuity chart and reported in ETDRS letters. [Time frame: Visit 1, Visit 2 and Study Termination Visit];

- *Patient reported outcomes:*

Change in intensity^{##} and frequency of dry eye symptoms assessed by completing the questionnaire SANDE. [Time frame: Visit 1, Visit 2 and Study Termination Visit].

^{##}In the questionnaire SANDE, the term "intensity" has the same meaning than "severity".

- ^{###}Evaluation of the degree of satisfaction to the treatment reported by patients through the use of the visual analogue scale (VAS) ^{###}, ranging from 0 to 100 mm, at Study Termination Visit (*Day 35 ± 4 of treatment*). [Time frame: Study Termination Visit].

Patients will be asked to rate their degree of satisfaction to the treatment and answer the following questions:

- “I feel satisfied using this treatment? ”,
- “With this treatment, I have a feeling of freshness?”,
- “With this treatment, I have a feeling of relief?”,

Study code: 052/SI Hyalistil Bio PF Mono

- “This treatment contributed to reduce my pain due to eye dryness?”,
- “This treatment is comfortable? ”,

Patients will be asked to place a vertical mark on a horizontal line, from 0 to 100 mm, to indicate the degree of satisfaction to the treatment, where:

- ✓ 0-10 mm=none
- ✓ 11-30 mm=very mild
- ✓ 31-50 mm=mild
- ✓ 51-70 mm=moderate
- ✓ 71-90 mm=strong
- ✓ 91-100 mm=very strong.

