13.2 Secondary objective

The secondary objectives were:

Clinical Performance

- Changes in NEI score from baseline will be summarized as minimum, maximum, mean,

Study code: 052/SI Hyalistil Bio PF Mono

standard deviation or median and IQR. Paired t-test or Wilcoxon signed-rank test will be used to test the statistical significance of the change from baseline to each timepoints. [Time frame: Visit 1, Visit 2 and Study Termination Visit].

The cornea is divided into five sectors (central, superior, inferior, nasal and temporal), each of which is scored on a scale of 0–3, with a maximal score of 15. Both nasally and temporally, the conjunctiva is divided into a superior paralimbal area, an inferior paralimbal area and a peripheral area with a grading scale of 0–3 and with a maximal total score of 18 for the nasal and temporal conjunctiva.

For a better reading it is also essential not to use an intense illumination beam, which may reduce the contrast and lead to an underestimation of grading.

- Changes in TFBUT from baseline will be reported as minimum, maximum, mean standard deviation or median and IQR. Paired t-test or Wilcoxon signed-rank will be used to test the statistical significance of the change from baseline to each timepoints. [Time frame: Visit 2, and Study Termination Visit].
- Change in the BVCA scores will be summarized as minimum, maximum, mean, standard deviation or median and IQR. Paired t-test or Wilcoxon signed-rank test will be used to test the statistical significance. Details of changes (i.e., difference in BVCA scores between baseline and end of treatment) will be summarized as well. [Time frame: Visit 1, Visit 2 and Study Termination Visit].
- Best Corrected Visual Acuity BCVA was measured using the standard Early Treatment Diabetic Retinopathy Study (ETDRS) acuity chart lighting, and procedures and reported in Best-corrected visual acuity is measured at all trial visits using standard charts, (chart 1 is used for testing the visual acuity of the RIGHT eye; Chart 2 for testing the LEFT eye). Patients should not be allowed to see any of the charts before the examination.

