5 PERFORMANCE DATA (SECONDARY ENDPOINTS)

-NEI Scale ITT population

Table 5.1.1 TOTAL SCORE NEI ITT population (v1) vs (v3)

Table 5.2.1 TOTAL SCORE NEI ITT population (v1) vs (v2)

Table 5.3.1 TOTAL SCORE CORNEA ITT population (v1) vs (v3)

Table 5.3.2 TOTAL SCORE CORNEA ITT population (v1) vs (v2)

Table 5.4.1 TOTAL SCORE CONJUNCTIVA ITT population (v1) vs (v3)

Table 5.4.2 TOTAL SCORE CONJUNCTIVA ITT population (v1) vs (v2)

-TFBUT ITT POPULATION

Table 5.5.1 TFBUT ITT population (v1) vs (v2)

-Questionnaire SANDE ITT population

Table 5.6.1 TOTAL SCORE SANDE ITT population (v1) vs (v3)

Table 5.7.1 TOTAL SCORE SANDE ITT population (v1) vs (v2)

Study code: 052/SI Hyalistil Bio PF Mono

Table 5.8.1 SEVERITY DRYNESS/IRRITATION ITT population (v1) vs (v3)

Table 5.8.2 SEVERITY DRYNESS/IRRITATION ITT population (v1) vs (v2)

Table 5.9.1 FREQUENCY DRYNESS/IRRITATION ITT population (v1) vs (v3)

Table 5.9.2 FREQUENCY DRYNESS/IRRITATION ITT population (v1) vs (v2)

-Questionnaire VAS ITT population

Table 5.10.1 Question "I feel satisfied using this treatment? ", ITT population

Table 5.10.2 Question "With this treatment, I have a feeling of freshness?", ITT population.

Table 5.10.3 Question "With this treatment, I have a feeling of relief?", ITT

Table 5.10.4 Question "This treatment contributed to reduce my pain due to eye dryness?", ITT population

Table 5.10.5 Question "This treatment is comfortable? ", ITT population

Table 5.10.6 Total score VAS, ITT population

-DEQS ITT POPULATION

Table 5.11.1.1 DEQS Summary score ITT population (v1) vs (v3)

Table 5.11.2.1 DEQS Bothersome Ocular Symptoms subscale ITT population (v1) vs (v3)

Table 5.11.3.1 DEQS Impact on Daily Life subscale ITT population (v1) vs (v3)

Table 5.11.4.1 DEQS-GES ITT population (v1) vs (v3)

-IGAS

Table 5.12.1 IGAS ITT populations

-IOP ITT POPULATION

Table 5.13.1 IOP ITT population (v1) vs (v3)

Table 5.14.1 IOP ITT population (v1) vs (v2)

Study code: 052/SI Hyalistil Bio PF Mono

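### No comparison of TFBUT at Study Termination with Visit 2 is pre-specified, although it is a stated secondary objective

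*SAP*

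**What the plan says.** V1, V2 and V3 stand for Visit 1 (baseline), Visit 2 (day 14) and the Study Termination Visit (day 35).

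- **Objective.** SAP 3.2 sets "TFBUT) at Study Termination Visit (*Day 35 ± 4 of treatment*) compared to Visit 2" as the comparison. Protocol section 11 and the protocol synopsis carry the same objective.
- **Endpoint.** SAP 5.2 lists secondary TFBUT with "Time frame: Visit 2 and Study Termination Visit" and names no contrast. Protocol section 19 does the same.
- **Analysis text.** SAP 13.2 says "Changes in TFBUT from baseline will be reported as minimum, maximum, mean standard deviation or median and IQR", and the test is of the "change from baseline to each timepoints. [Time frame: Visit 2, and Study Termination Visit". Protocol section 23 has the same analysis. The general test rule in SAP 10 also sets baseline against the other timepoints.
- **Comparisons to be tabulated.** SAP 15 gives "visit 2 versus visit 1 and visit 3 versus visit 1", with the difference also expressed as a percentage from baseline.
- **Tables.** The primary TFBUT tables (4.1.1 to 4.2.2) are V1 against V3. The one secondary TFBUT table is "Table 5.5.1 TFBUT ITT population (v1) vs (v2)", and its shell shows the V2 minus V1 difference.
- **Missing data.** Under SAP 10.2.5 and Protocol section 23, a missing V2 value takes the baseline value. A missing V3 value takes the V2 value or, failing that, the baseline value.

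**The concern.** The contrast in the objective and the contrasts in the analysis are different quantities. V2-V1 describes the early gain over the first two weeks, and V3-V1 is the primary comparison. Neither tests whether TFBUT changes between day 14 and day 35, which is what the objective asks. Followed as written, the plan puts V2-V1 in the place of V3-V2, and its baseline-to-termination test under the secondary item repeats the primary analysis.

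At stake is one secondary objective that would reach the report without its own estimate of precision or test, or with one chosen after the data were seen. The SAP is dated 10 October 2023 and gives 3 August 2023 as the last patient's last visit. An unplanned addition would therefore be open to the charge of being post hoc.

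**Working it through.** **Step 1: objective against plan.**

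| TFBUT contrast | In an objective? | In the analysis text? | In a table? |
|---|---|---|---|
| V3-V1 | Yes (primary) | Yes | 4.1.1 to 4.2.2 |
| V2-V1 | No | Yes | 5.5.1 |
| V3-V2 | Yes (secondary) | No | None |

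**Step 2: what the planned tables still give.** The shells of Tables 4.1.1 and 5.5.1 report N, mean, SD, median and quartiles at each visit, both in the ITT population. With the same patients in both:

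mean(V3-V2) = mean(V3) - mean(V2)

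The point estimate of the mean change is therefore available. The median of the paired differences is not, because medians do not subtract.

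**Step 3: what they do not give.** The variance is

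Var(V3-V2) = Var(V3) + Var(V2) - 2 Cov(V2, V3)

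The tables give the SD at each visit and the SDs of V3-V1 and V2-V1. None gives the V2-V3 covariance. To show how much depends on it, write s for the SD of each change from baseline and r for the correlation between the two changes. Then SD(V3-V2) = s × √(2(1 - r)). I take s = 1.91, the SD in the sample-size section, and assume that it holds for both changes. With n = 23, the 95% half-width is 2.074 × SD/√23 (t quantile on 22 degrees of freedom).

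| r (assumed) | SD(V3-V2), s | 95% half-width, s |
|---|---|---|
| 0 | 2.70 | 1.17 |
| 0.5 | 1.91 | 0.83 |
| 0.8 | 1.21 | 0.52 |
| 0.9 | 0.85 | 0.37 |

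The half-width varies about threefold over this range, so the precision cannot be guessed from the planned output.

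**Step 4: effect of the imputation rule on V3-V2.**
- V3 missing, V2 observed: V3 is set to V2, so V3-V2 = 0 exactly.
- V2 missing, V3 observed: V2 is set to V1, so V3-V2 becomes V3-V1.
- Both missing: both equal baseline, so V3-V2 = 0.

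The plan enrols 28 for 23 evaluable, which allows for 28 - 23 = 5 losses. If all 5 lacked only V3 and remained in the ITT set, the imputed mean would be 23/28 = 0.82 of the observed-case mean, a shrinkage of 5/28 = 18%. A missing V2 instead inserts a whole baseline-to-termination change, which the plan puts at 1.56 s on average. The mean obtained by subtraction in Step 2 carries the same distortion.

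**Step 5: the plan's only related figure.** The sample size concerns V3-V1. With 1.56/1.91 = 0.817, two-sided alpha 0.01 and power 0.80, a paired t-test needs 21. Multiplying by π/3 for the signed-rank test gives 21.99, so 22 against the stated 23. It reproduces closely, and the present point does not touch it.

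**The case against.** - **The table list is open.** SAP 15 says that its lists may be incomplete and that tables can be added. This stands against any claim that the contrast will never be analysed. It does not make the contrast pre-specified, and the next paragraph names only the two baseline comparisons.
- **The time frame hints at V2 against V3.** The secondary TFBUT item omits Visit 1, while the staining, visual acuity and SANDE items include it. The baseline wording may be carried over from those items. That is plausible, and it makes the text contradictory rather than silent. But the test itself is defined as a change from baseline.
- **The result is largely recoverable.** The mean change follows by subtraction, and patient-level listings are planned. This holds, and it limits the size of the point. It supplies no SD, interval or test, and a listing is not an analysis.
- **The objective may be the faulty text.** It speaks of tear film stability per group, yet the study has one open-label treatment and SAP 10.1 says that there are no subgroups. The objective could be leftover wording. This stands, so the reconciliation may go either way.

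A reader might also infer that the SAP departs from the protocol. It does not: Protocol section 23 contains the same mismatch between objective and analysis.

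**Conclusion.** The point holds in limited form: a stated secondary objective has no pre-specified analysis of its own contrast, in either document. What is missing is the SD, confidence interval and p-value of V3-V2. The mean is obtainable, subject to the imputation effect.

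The documents do not support the stronger reading that the trial cannot answer the objective. TFBUT is measured at both visits, both visit means are tabulated, and further tables are allowed. Nor do they support any effect on the primary endpoint or the sample size.

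The mismatch itself rests on the text alone. The half-widths in Step 3 assume equal SDs of 1.91 and a correlation that the documents do not give. The 18% shrinkage assumes that all five allowed losses lack V3 only. This should be corrected, but it is confined to one secondary objective.

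**What to change.** - In SAP 13.2, add a paired V3-V2 TFBUT analysis with the estimated change, its 95% confidence interval and the test chosen by the plan's existing distribution rule. Add the matching table to SAP 15.2, and include V3-V2 for TFBUT among the comparisons in SAP 15.
- Base it on patients with both visits observed. Give the imputed ITT version as a sensitivity analysis, and say how differences that are zero by imputation are treated.
- Align Protocol section 23. Keep Table 5.5.1 as supportive.
- If only the baseline contrasts were intended, amend the objective instead in the protocol (synopsis and section 11) and in SAP 3.2.

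Either route should be dated and completed before database lock, which SAP 6.2 describes as still to come. The cost is a short text change and, for the first route, one main table with its sensitivity version, from data already collected.

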15.1 LIST AND SAMPLES OF FIGURES

1 DISPOSITION OF PATIENTS

Figure 1 Patient's disposition by CONSORT.

15.2 LIST AND SAMPLES OF TABLES

1 TREATMENT DURATION

Table 1 Treatment duration ITT population

2 DEMOGRAPHICS AND OTHER BASELINE DATA

Table 2.1.1 Demographic characteristics (screened patients) Age

Table 2.1.2 Demographic characteristics of Age

Table 2.1.2 Demographic characteristics (screened patients) Sex

Table 2.1.3 Demographic characteristics (screened patients) Race

Table 2.2.1 Demographic characteristics (ITT population) Age

Table 2.2.2 Demographic characteristics (ITT population) Sex

Table 2.2.3 Demographic characteristics (ITT population) Race

Table 2.3.1 Demographic characteristics (PP population) Age

Table 2.3.2 Demographic characteristics (PP population) Sex

Table 2.3.3 Demographic characteristics (PP population) Race

Table 2.4.2.1 Medical history (Visit 1: ITT population)

Table 2.4.2.2 Medical history (Visit 2: ITT population)

Table 2.4.2.3 Medical history (Visit 3: ITT population)

Table 2.4.2.4 Concomitant medications (ITT population)

Table 2.4.3.1 Medical history (Visit 1: PP population)

Table 2.4.3.2 Medical history (Visit 2: PP population)

Table 2.4.3.3 Medical history (Visit 3: PP population)

Table 2.4.3.4 Concomitant medications (PP population)

3 COMPLIANCE DATA

Table 3.1 % Administered doses over the planned doses (ITT population)

Table 3.2 % Administered doses over the planned doses (PP population)

4 PERFORMANCE DATA (PRIMARY ENDPOINTS)

Table 4.1.1 TFBUT ITT population (v1) vs (v3)

Table 4.1.2 Delta % TFBUT ITT population (v1) vs (v3)

Table 4.2.1 TFBUT PP population (v1) vs (v3)

Table 4.2.2 Delta % TFBUT PP population (v1) vs (v3)

5 PERFORMANCE DATA (SECONDARY ENDPOINTS)

-NEI Scale ITT population

Table 5.1.1 TOTAL SCORE NEI ITT population (v1) vs (v3)

Table 5.2.1 TOTAL SCORE NEI ITT population (v1) vs (v2)

Table 5.3.1 TOTAL SCORE CORNEA ITT population (v1) vs (v3)

Table 5.3.2 TOTAL SCORE CORNEA ITT population (v1) vs (v2)

Table 5.4.1 TOTAL SCORE CONJUNCTIVA ITT population (v1) vs (v3)

Table 5.4.2 TOTAL SCORE CONJUNCTIVA ITT population (v1) vs (v2)

-TFBUT ITT POPULATION

Table 5.5.1 TFBUT ITT population (v1) vs (v2)

-Questionnaire SANDE ITT population

Table 5.6.1 TOTAL SCORE SANDE ITT population (v1) vs (v3)

Table 5.7.1 TOTAL SCORE SANDE ITT population (v1) vs (v2)

Study code: 052/SI Hyalistil Bio PF Mono

Table 5.8.1 SEVERITY DRYNESS/IRRITATION ITT population (v1) vs (v3)

Table 5.8.2 SEVERITY DRYNESS/IRRITATION ITT population (v1) vs (v2)

Table 5.9.1 FREQUENCY DRYNESS/IRRITATION ITT population (v1) vs (v3)

Table 5.9.2 FREQUENCY DRYNESS/IRRITATION ITT population (v1) vs (v2)

-Questionnaire VAS ITT population

Table 5.10.1 Question "I feel satisfied using this treatment? ", ITT population

Table 5.10.2 Question "With this treatment, I have a feeling of freshness?", ITT population.

Table 5.10.3 Question "With this treatment, I have a feeling of relief?", ITT

Table 5.10.4 Question "This treatment contributed to reduce my pain due to eye dryness?", ITT population

Table 5.10.5 Question "This treatment is comfortable? ", ITT population

Table 5.10.6 Total score VAS, ITT population

-DEQS ITT POPULATION

Table 5.11.1.1 DEQS Summary score ITT population (v1) vs (v3)

Table 5.11.2.1 DEQS Bothersome Ocular Symptoms subscale ITT population (v1) vs (v3)

Table 5.11.3.1 DEQS Impact on Daily Life subscale ITT population (v1) vs (v3)

Table 5.11.4.1 DEQS-GES ITT population (v1) vs (v3)

-IGAS

Table 5.12.1 IGAS ITT populations

-IOP ITT POPULATION

Table 5.13.1 IOP ITT population (v1) vs (v3)

Table 5.14.1 IOP ITT population (v1) vs (v2)

Study code: 052/SI Hyalistil Bio PF Mono

16. LIST OF LISTING

[figure not shown]
Listing 1 ITT Population datasets

Listing 2 PP Population datasets

Listing 3 ITT Population datasets DEQS

Listing 4 ITT Population datasets VAS

FIGURE 1: Patient deposition

Study code: 052/SI Hyalistil Bio PF Mono

Table 1

ITT population

Analysis variable: Treatment duration							
Mean	Std Dev	Min	Max	N	lower quartile	Median	upper quartile
X.XX	X.XX	X.XX	X.XX	XX	X.XX	X.XX	X.XX

Test for Normality				
Test		Statistic		P-value
Shapiro-Wilk	W	x.xxx	Pr < W	x.xxx
Kolmogorov-Smirnov	D	x.xxx	Pr > D	x.xxx
Cramer-von Mises	W-Qu	x.xxx	Pr > W-Qu	x.xxx
Anderson-Darling	A-Qu	x.xxx	Pr > A-Qu	x.xxx

Program SAS 9.4 ('Local', X64_10HOME) date xx XXXX xxxx

Study code: 052/SI Hyalistil Bio PF Mono

Table 2.1.1 Demographics and other baseline data

Screened patients							
Analysis variable: Age							
Mean	Std Dev	Min	Max	N	lower quartile	Median	upper quartile
X.XX	X.XX	X.XX	X.XX	XX	X.XX	X.XX	X.XX

Test for Normality				
	Test	Statistic	P-value	
Shapiro-Wilk	W	X.XXX	Pr < W	X.XXX
Kolmogorov-Smirnov	D	X.XXX	Pr > D	X.XXX
Cramer-von Mises	W-Qu	X.XXX	Pr > W-Qu	X.XXX
Anderson-Darling	A-Qu	X.XXX	Pr > A-Qu	X.XXX

Program SAS 9.4 ('Local', X64_10HOME) date xx XXX xxxx

Study code: 052/SI Hyalistil Bio PF Mono

Table 2.1.2 Demographics and other baseline data

Screened patients

Sex

	N	%
Male	X	xx.xx
Female	X	xx.xx

Program SAS 9.4 ('Local', X64_10HOME) date xx XXX xxxx

Table 2.1.3 Demographics and other baseline data

Screened patients

Race

	N	%
Caucasian	X	xx.xx
Xxxxx	X	xx.xx
Xxxxx	X	xx.xx

Program SAS 9.4 ('Local', X64_10HOME) date xx XXX xxxx

Table 2.2.1 Demographics and other baseline data

ITT population

Analysis variable: Age							
Mean	Std Dev	Min	Max	N	lower quartile	Median	upper quartile
X.XX	X.XX	X.XX	X.XX	XX	X.XX	X.XX	X.XX

Test for Normality

	Test		Statistic		P-value
	Shapiro-Wilk	W	X.XXX	Pr < W	X.XXX
	Kolmogorov-Smirnov	D	X.XXX	Pr > D	X.XXX
	Cramer-von Mises	W-Qu	X.XXX	Pr > W-Qu	X.XXX
	Anderson-Darling	A-Qu	X.XXX	Pr > A-Qu	X.XXX

Age (classes, years)

N *%*

[18-64]	X	XX.XX
>65	X	XX.XX

Age by sex

Analysis variable: Age males

Mean	Std Dev	Min	Max	N	lower quartile	Median	upper quartile
X.XX	X.XX	X.XX	X.XX	XX	X.XX	X.XX	X.XX

Test for Normality

Hyalistil Bio PF Mono
Medical device

Study code: 052/SI Hyalistil Bio PF Mono

	Test		Statistic		P-value
	Shapiro-Wilk	W	x.xxx	Pr < W	x.xxx
	Kolmogorov-Smirnov	D	x.xxx	Pr > D	x.xxx
	Cramer-von Mises	W-Qu	x.xxx	Pr > W-Qu	x.xxx
	Anderson-Darling	A-Qu	x.xxx	Pr > A-Qu	x.xxx

Analysis variable: Age females

Mean	Std Dev	Min	Max	N	lower quartile	Median	upper quartile
x.xx	x.xx	x.xx	x.xx	xx	x.xx	x.xx	x.xx

Test for Normality

	Test		Statistic		P-value
	Shapiro-Wilk	W	x.xxx	Pr < W	x.xxx
	Kolmogorov-Smirnov	D	x.xxx	Pr > D	x.xxx
	Cramer-von Mises	W-Qu	x.xxx	Pr > W-Qu	x.xxx
	Anderson-Darling	A-Qu	x.xxx	Pr > A-Qu	x.xxx

Program SAS 9.4 ('Local', X64_10HOME) date xx XXX xxxx

Study code: 052/SI Hyalistil Bio PF Mono

Table 2.2.2 Demographics and other baseline data

ITT population		
Sex		
	N	%
Male	x	xx.xx
Female	x	xx.xx

Program SAS 9.4 ('Local', X64_10HOME) date xx XXX xxxx

Table 2.2.3 Demographics and other baseline data

ITT population		
Race		
	N	%
Caucasian	x	xx.xx
xxxxx	x	xx.xx
xxxxx	x	xx.xx

Program SAS 9.4 ('Local', X64_10HOME) date xx XXX xxxx

Study code: 052/SI Hyalistil Bio PF Mono

Table 2.3.1 Demographics and other baseline data
PP population

Analysis variable: Age										
Mean	Std Dev	Min	Max	N	lower quartile	Median	upper quartile			
X.XX	X.XX	X.XX	X.XX	XX	X.XX	X.XX	X.XX			
<hr/>										
Test for Normality										
Test		Statistic			P-value					
Shapiro-Wilk		W	x.xxx	Pr < W	x.xxx					
Kolmogorov-Smirnov		D	x.xxx	Pr > D	x.xxx					
Cramer-von Mises		W-Qu	x.xxx	Pr > W-Qu	x.xxx					
Anderson-Darling		A-Qu	x.xxx	Pr > A-Qu	x.xxx					
<hr/>										
Age (classes, years)										
N				%						
[18-64]		x	xx.xx							
>65		x	xx.xx							

Program SAS 9.4 ('Local', X64_10HOME) date xx XXXX xxxx

Table 2.3.2 Demographics and other baseline data

Study code: 052/SI Hyalistil Bio PF Mono

PP population
Sex

	N	%
Male	x	xx.xx
Female	x	xx.xx

Program SAS 9.4 ('Local', X64_10HOME) date xx XXX xxxx

Study code: 052/SI Hyalistil Bio PF Mono

Table 2.3.3 Demographics and other baseline data

PP population		
Race		
	N	%
Caucasian	x	xx.xx
xxxxx	x	xx.xx
xxxxx	x	xx.xx

Program SAS 9.4 ('Local', X64_10HOME) date xx XXX xxxx

Study code: 052/SI Hyalistil Bio PF Mono

Table 2.4.2.1 Demographics and other baseline data

ITT population		
Medical history (Visit 1)		
	N	%
xxxxx	x	xx.xx

Program SAS 9.4 ('Local', X64_10HOME) date xx XXX xxxx

Table 2.4.2.2 Demographics and other baseline data

ITT population		
Medical history (Visit 2)		
	N	%
xxxxx	x	xx.xx

Program SAS 9.4 ('Local', X64_10HOME) date xx XXX xxxx

Study code: 052/SI Hyalistil Bio PF Mono

Table 2.4.2.3 Demographics and other baseline data

ITT population		
Medical history (Visit 3)		
	N	%
xxxxx	x	xx.xx

Program SAS 9.4 ('Local', X64_10HOME) date xx XXX xxxx

Table 2.4.2.4 Demographics and other baseline data

ITT population		
Concomitant medications		
	N	%
xxxxx	x	xx.xx

Program SAS 9.4 ('Local', X64_10HOME) date xx XXX xxxx

Study code: 052/SI Hyalistil Bio PF Mono

Table 2.4.3.1 Demographics and other baseline data

PP population		
Medical history (Visit 1)		
	N	%
xxxxx	x	xx.xx

Program SAS 9.4 ('Local', X64_10HOME) date xx XXX xxxx

Table 2.4.3.2 Demographics and other baseline data

PP population		
Medical history (Visit 2)		
	N	%
xxxxx	x	xx.xx

Program SAS 9.4 ('Local', X64_10HOME) date xx XXX xxxx

Study code: 052/SI Hyalistil Bio PF Mono

Table 2.4.3.3 Demographics and other baseline data

PP population		
Medical history (Visit 3)		
	N	%
xxxxx	x	xx.xx

Program SAS 9.4 ('Local', X64_10HOME) date xx XXX xxxx

Table 2.4.3.4 Demographics and other baseline data

PP population		
Concomitant medications		
	N	%
xxxxx	x	xx.xx

Program SAS 9.4 ('Local', X64_10HOME) date xx XXX xxxx

Study code: 052/SI Hyalistil Bio PF Mono

Table 3.1 % Administered doses over the planned doses

ITT population		
% Administered doses over the planned doses		
	N	%
xxxxx	x	xx.xx
<50 % Poor Compliance	x	xx.xx
50-80 % Moderate Compliance	x	xx.xx
> 80 % Good Compliance	x	xx.xx

Program SAS 9.4 ('Local', X64_10HOME) date xx XXX xxxx

Table 3.2 % Administered doses over the planned doses

PP population		
% Administered doses over the planned doses		
	N	%
xxxxx	x	xx.xx
<50 % Poor Compliance	x	xx.xx
50-80 % Moderate Compliance	x	xx.xx
> 80 % Good Compliance	x	xx.xx

Program SAS 9.4 ('Local', X64_10HOME) date xx XXX xxxx

Table 4.1.1 TFBUT ITT population (v1) vs (v3)

ITT population

TFBUT v1 vs v3

Variable: TFBUT Visit 1

Test for Normality							
Test		Statistic		P-value			
Shapiro-Wilk		W	x.xxxx	Pr < W		x.xxxx	
Kolmogorov-Smirnov	D		x.xxxx	Pr > D		x.xxxx	
Cramer-von Mises		W-Qu	x.xxxx	Pr > W-Qu		x.xxxx	
Anderson-Darling		A-Qu	x.xxxx	Pr > A-Qu		x.xxxx	
<hr/>							
N	Mean	Std dev	Min	Max	Lower quartile	Median	Upper quartile
x	x.xx	x.xx	x.xx	x.xx	x.xx	x.xx	x.xx
<hr/>							

Variable: TFBUT Visit 3

Test for Normality							
Test		Statistic		P-value			
Shapiro-Wilk		W	x.xxxx	Pr < W		x.xxxx	
Kolmogorov-Smirnov	D		x.xxxx	Pr > D		x.xxxx	
Cramer-von Mises		W-Qu	x.xxxx	Pr > W-Qu		x.xxxx	
Anderson-Darling		A-Qu	x.xxxx	Pr > A-Qu		x.xxxx	
<hr/>							
N	Mean	Std dev	Min	Max	Lower quartile	Median	Upper quartile
x	x.xx	x.xx	x.xx	x.xx	x.xx	x.xx	x.xx
<hr/>							

Hyalistil Bio PF Mono
Medical device

Study code: 052/SI Hyalistil Bio PF Mono

Variable: Difference TFBUT Visit 3 – Visit 1

Basic Statistical Measures					
Location			Variability		
Mean	x.xx	Std dev	x.xx		
Median	x.xx	Variance	x.xx		
Mode	x.xx	Range	x.xx		
Interquartile range			x.xx		
Location test: Mu0=0					
Test	Statistic		P-value		
Student's T	t	x.xxx	Pr > t	x.xxxx	
sign	M	xx	Pr >= M	x.xxxx	
Signed rank	S	x.xxx	Pr >= S	x.xxxx	

Program SAS 9.4 ('Local', X64_10HOME) date xxXXxxxx

Table 4.1.2 Delta % TFBUT ITT population v1-v3

Analysis variable: Delta % TFBUT v1-v3

Mean	Std Dev				Lower quartile	Median	Upper quartile
		Min	Max	N			
x.xx	x.xx	x.xx	x.xx	xx	x.xx	x.xx	x.xx

Program SAS 9.4 ('Local', X64_10HOME) date xxXXxxxx

Study code: 052/SI Hyalistil Bio PF Mono

Table 4.2.1 TFBUT PP population (v1) vs (v3)

PP population
TFBUT v1 vs v3

Variable: TFBUT Visit 1

Test for Normality							
Test		Statistic		P-value			
Shapiro-Wilk		W	x.xxxx	Pr < W		x.xxxx	
Kolmogorov-Smirnov	D		x.xxxx	Pr > D		x.xxxx	
Cramer-von Mises		W-Qu	x.xxxx	Pr > W-Qu		x.xxxx	
Anderson-Darling		A-Qu	x.xxxx	Pr > A-Qu		x.xxxx	
<hr/>							
N	Mean	Std dev	Min	Max	Lower quartile	Median	Upper quartile
x	x.xx	x.xx	x.xx	x.xx	x.xx	x.xx	x.xx
<hr/>							

Variable: TFBUT Visit 3

Test for Normality							
Test		Statistic		P-value			
Shapiro-Wilk		W	x.xxxx	Pr < W		x.xxxx	
Kolmogorov-Smirnov	D		x.xxxx	Pr > D		x.xxxx	
Cramer-von Mises		W-Qu	x.xxxx	Pr > W-Qu		x.xxxx	
Anderson-Darling		A-Qu	x.xxxx	Pr > A-Qu		x.xxxx	
<hr/>							
N	Mean	Std dev	Min	Max	Lower quartile	Median	Upper quartile
x	x.xx	x.xx	x.xx	x.xx	x.xx	x.xx	x.xx
<hr/>							

Variable: Difference TFBUT Visit 3 – Visit 1

Hyalistil Bio PF Mono
Medical device

Study code: 052/SI Hyalistil Bio PF Mono

Basic Statistical Measures

Location	Variability		
Mean	x.xx	Std dev	x.xx
Median	x.xx	Variance	x.xx
Mode	x.xx	Range	x.xx
Interquartile range		x.xx	

Location test: Mu0=0

Test	Statistic	P-value
Student's T	t	x.xxx
sign	M	xx
Signed rank	S	x.xxx
		Pr >= M
		xxxxx
		Pr >= S
		xxxxx

Program SAS 9.4 ('Local', X64_10HOME) date xxXXXXXX

Table 4.2.2 Delta % TFBUT PP population v1-v3

Analysis variable: Delta % TFBUT v1-v3

Mean	Std Dev	Min	Max	N	Lower quartile	Median	Upper quartile
x.xx	x.xx	x.xx	x.xx	xx	x.xx	x.xx	x.xx

Table 5.1.1 TOTAL SCORE NEI ITT population (v1) vs (v3)

ITT population

TOTAL SCORE NEI v1 vs v3

Variable TOTAL SCORE NEI Visit 1

Test for Normality							
Test		Statistic		P-value			
Shapiro-Wilk		W	x.xxxx	Pr < W		x.xxxx	
Kolmogorov-Smirnov	D		x.xxxx	Pr > D		x.xxxx	
Cramer-von Mises		W-Qu	x.xxxx	Pr > W-Qu		x.xxxx	
Anderson-Darling		A-Qu	x.xxxx	Pr > A-Qu		x.xxxx	
<hr/>							
N	Mean	Std dev	Min	Max	Lower quartile	Median	Upper quartile
x	x.xx	x.xx	x.xx	x.xx	x.xx	x.xx	x.xx
<hr/>							

Variable: TOTAL SCORE NEI Visit 3

Test for Normality							
Test		Statistic		P-value			
Shapiro-Wilk		W	x.xxxx	Pr < W		x.xxxx	
Kolmogorov-Smirnov	D		x.xxxx	Pr > D		x.xxxx	
Cramer-von Mises		W-Qu	x.xxxx	Pr > W-Qu		x.xxxx	
Anderson-Darling		A-Qu	x.xxxx	Pr > A-Qu		x.xxxx	
<hr/>							
N	Mean	Std dev	Min	Max	Lower quartile	Median	Upper quartile
x	x.xx	x.xx	x.xx	x.xx	x.xx	x.xx	x.xx
<hr/>							

Hyalistil Bio PF Mono
Medical device

Study code: 052/SI Hyalistil Bio PF Mono

Variable: Difference TOTAL SCORE NEI Visit 3 – Visit 1

Basic Statistical Measures

Location	Variability		
Mean	x.xx	Std dev	x.xx
Median	x.xx	Variance	x.xx
Mode	x.xx	Range	x.xx
		Interquartile range	x.xx

Location test: Mu0=0

Test	Statistic	P-value		
Student's T	t	x.xxx	Pr > t	x.xxxx
sign	M	xx	Pr >= M	x.xxxx
Signed rank	S	x.xxx	Pr >= S	x.xxxx

Program SAS 9.4 ('Local', X64_10HOME) date xxXXXXxxx

Study code: 052/SI Hyalistil Bio PF Mono

Table 5.2.1 TOTAL SCORE NEI ITT population (v1) vs (v2)

ITT population
TOTAL SCORE NEI v1 vs v2

Variable TOTAL SCORE NEI Visit 1

Test for Normality							
Test		Statistic		P-value			
Shapiro-Wilk		W	x.xxxx	Pr < W		x.xxxx	
Kolmogorov-Smirnov	D		x.xxxx	Pr > D		x.xxxx	
Cramer-von Mises		W-Qu	x.xxxx	Pr > W-Qu		x.xxxx	
Anderson-Darling		A-Qu	x.xxxx	Pr > A-Qu		x.xxxx	
<hr/>							
N	Mean	Std dev	Min	Max	Lower quartile	Median	Upper quartile
x	x.xx	x.xx	x.xx	x.xx	x.xx	x.xx	x.xx
<hr/>							

Variable: TOTAL SCORE NEI Visit 2

Test for Normality							
Test		Statistic		P-value			
Shapiro-Wilk		W	x.xxxx	Pr < W		x.xxxx	
Kolmogorov-Smirnov	D		x.xxxx	Pr > D		x.xxxx	
Cramer-von Mises		W-Qu	x.xxxx	Pr > W-Qu		x.xxxx	
Anderson-Darling		A-Qu	x.xxxx	Pr > A-Qu		x.xxxx	
<hr/>							
N	Mean	Std dev	Min	Max	Lower quartile	Median	Upper quartile
x	x.xx	x.xx	x.xx	x.xx	x.xx	x.xx	x.xx
<hr/>							

Variable: Difference TOTAL SCORE NEI Visit 2 – Visit 1

Hyalistil Bio PF Mono
Medical device

Study code: 052/SI Hyalistil Bio PF Mono

Basic Statistical Measures

Location	Variability		
Mean	x.xx	Std dev	x.xx
Median	x.xx	Variance	x.xx
Mode	x.xx	Range	x.xx
Interquartile range			x.xx

Location test: Mu0=0

Test	Statistic	P-value
Student's T	t x.xxx	Pr > t x.xxxx
sign	M xx	Pr >= M x.xxxx
Signed rank	S x.xxx	Pr >= S x.xxxx

Program SAS 9.4 ('Local', X64_10HOME) date xxXXXXxxx

Study code: 052/SI Hyalistil Bio PF Mono

Table 5.3.1 TOTAL SCORE CORNEA ITT population (v1) vs (v3)

ITT population
TOTAL SCORE CORNEA v1 vs v3

Variable TOTAL SCORE CORNEA Visit 1

Test for Normality							
Test		Statistic		P-value			
Shapiro-Wilk		W	x.xxxx	Pr < W		x.xxxx	
Kolmogorov-Smirnov	D		x.xxxx	Pr > D		x.xxxx	
Cramer-von Mises		W-Qu	x.xxxx	Pr > W-Qu		x.xxxx	
Anderson-Darling		A-Qu	x.xxxx	Pr > A-Qu		x.xxxx	
N	Mean	Std dev	Min	Max	Lower quartile	Median	Upper quartile
x	x.xx	x.xx	x.xx	x.xx	x.xx	x.xx	x.xx

Variable: TOTAL SCORE CORNEA Visit 3

Test for Normality							
Test		Statistic		P-value			
Shapiro-Wilk		W	x.xxxx	Pr < W		x.xxxx	
Kolmogorov-Smirnov	D		x.xxxx	Pr > D		x.xxxx	
Cramer-von Mises		W-Qu	x.xxxx	Pr > W-Qu		x.xxxx	
Anderson-Darling		A-Qu	x.xxxx	Pr > A-Qu		x.xxxx	
N	Mean	Std dev	Min	Max	Lower quartile	Median	Upper quartile
x	x.xx	x.xx	x.xx	x.xx	x.xx	x.xx	x.xx

Variable: Difference TOTAL SCORE CORNEA Visit 3 – Visit 1

Hyalistil Bio PF Mono
Medical device

Study code: 052/SI Hyalistil Bio PF Mono

Basic Statistical Measures

Location	Variability		
Mean	x.xx	Std dev	x.xx
Median	x.xx	Variance	x.xx
Mode	x.xx	Range	x.xx
		Interquartile range	x.xx

Location test: Mu0=0

Test	Statistic	P-value		
Student's T	t	x.xxx	Pr > t	x.xxxx
sign	M	xx	Pr >= M	x.xxxx
Signed rank	S	x.xxx	Pr >= S	x.xxxx

Program SAS 9.4 ('Local', X64_10HOME) date xxXXXXxxx

Study code: 052/SI Hyalistil Bio PF Mono

Table 5.3.2 TOTAL SCORE CORNEA ITT population (v1) vs (v2)

ITT population
TOTAL SCORE CORNEA v1 vs v2

Variable TOTAL SCORE NEI Visit 1

Test for Normality							
Test		Statistic		P-value			
Shapiro-Wilk	W	x.xxxx	Pr < W	x.xxxx			
Kolmogorov-Smirnov	D	x.xxxx	Pr > D	x.xxxx			
Cramer-von Mises	W-Qu	x.xxxx	Pr > W-Qu	x.xxxx			
Anderson-Darling	A-Qu	x.xxxx	Pr > A-Qu	x.xxxx			
<hr/>							
N	Mean	Std dev	Min	Max	Lower quartile	Median	Upper quartile
x	x.XX	x.XX	x.XX	x.XX	x.XX	x.XX	x.XX
<hr/>							

Variable: TOTAL SCORE CORNEA Visit 2

Test for Normality							
Test		Statistic		P-value			
Shapiro-Wilk	W	x.xxxx	Pr < W	x.xxxx			
Kolmogorov-Smirnov	D	x.xxxx	Pr > D	x.xxxx			
Cramer-von Mises	W-Qu	x.xxxx	Pr > W-Qu	x.xxxx			
Anderson-Darling	A-Qu	x.xxxx	Pr > A-Qu	x.xxxx			
<hr/>							
N	Mean	Std dev	Min	Max	Lower quartile	Median	Upper quartile
x	x.XX	x.XX	x.XX	x.XX	x.XX	x.XX	x.XX
<hr/>							

Variable: Difference TOTAL SCORE CORNEA Visit 2 – Visit 1

Hyalistil Bio PF Mono
Medical device

Study code: 052/SI Hyalistil Bio PF Mono

Basic Statistical Measures

Location	Variability		
Mean	x.xx	Std dev	x.xx
Median	x.xx	Variance	x.xx
Mode	x.xx	Range	x.xx
		Interquartile range	x.xx

Location test: Mu0=0

Test	Statistic	P-value		
Student's T	t	x.xxx	Pr > t	xxxxx
sign	M	xx	Pr >= M	xxxxx
Signed rank	S	x.xxx	Pr >= S	xxxxx

Program SAS 9.4 ('Local', X64_10HOME) date xxXXXXxxx

Study code: 052/SI Hyalistil Bio PF Mono

Table 5.4.1 TOTAL SCORE CONJUNCTIVA ITT population (v1) vs (v3)

ITT population

TOTAL SCORE CONJUNCTIVA v1 vs v3

Variable TOTAL SCORE CONJUNCTIVA Visit 1

Test for Normality						
Test		Statistic		P-value		
Shapiro-Wilk	W	x.xxxx	Pr < W		x.xxxx	
